10.2 Subject Accountability

The number and percent of subjects who received IP (AMG 334 or placebo), completed study and discontinued the study (including reasons for discontinuing) will be summarized. A list of subjects who withdraw early will be reviewed. It will include the reason and timing of the withdrawal. Similarly, the reason any subject is excluded from an analysis set will also be reviewed.

10.3 Important Protocol Deviations

IPD categories are defined by the study team before the first subject's visit and updated during the IPD reviews throughout the study prior to database lock. These definitions of IPD categories, sub-category codes and descriptions will be used during the course of the study. Eligibility deviations are defined in the protocol.

The final IPD list will be used to produce the Summary of IPDs table and the list of subjects with IPDs. In addition, a separate listing of all inclusion and exclusion deviations will be provided.

Statistical Analysis Plan: 20140207

Date: 17 May 2017 Page 23

10.4 Demographic and Baseline Characteristics

The following demographic and baseline characteristics will be summarized.

Demographics:

• Age (years) at enrollment (continuous summary statistics)

- Age groups (years) [18-64, 65-74, 75-84, >=85] at enrollment (number and percentage of subjects in each age group category)
- Sex (number and percentage of males and females)
- Ethnicity (number and percentage in each ethnicity category)
- Race (number and percentage of subjects in each race, or mixed race combination)

Baseline Characteristics:

Height, Weight and BMI (continuous summary statistics)

10.5 Primary Endpoint Planned Analysis

The number and percent of subjects experiencing a MLA within 24 hours after PACAP-38 infusion will be summarized for each treatment group. Comparison of PACAP-38 ability to produce MLA between AMG 334 and placebo will be done using the Fisher's Exact test.

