8.2 Interim Analysis

Once 24 hours of data is collected from 16 PACAP-38 responders dosed with AMG 334 or Placebo (8 per group) after PACAP-38 infusion on Day 8, an interim analysis will be performed to determine if the challenge-agent, PACAP-38, invokes historical rates of MLA (~66%) and if AMG 334 has greater efficacy than placebo. If the number of MLAs does not meet historical rates, AMG 334 does not appear to be better at blocking PACAP-38 induced migraines compared with placebo, or AMG 334 appears to be sufficiently better at blocking PACAP-38 induced migraines compared with placebo, the study will be terminated (see below for more details). Otherwise, another 20 PACAP-38 responders will be randomized. Appropriate decision rules, outlined below were developed to determine whether to increase the sample size (another 20 responders dosed with AMG 334 or Placebo, 10 per treatment group) or to stop, either due to demonstration of treatment effect or treatment utility.

Decision rules to be applied during the trial are:

- At the interim analysis, if 3 or less of the 8 placebo subjects have a MLA, randomization will be stopped and it will be concluded that PACAP-38 does not induce a sufficient proportion of MLA for the study to test the hypothesis.
- 2. At the interim analysis, if 4 or more placebo subjects have a MLA, yet more subjects receiving AMG 334 have MLA than placebo subjects, then randomization will be stopped and it will be concluded that AMG 334 is ineffective in blocking PACAP-38 induced MLA.
- 3. If the difference at the interim analysis in the proportion of subjects with MLA (placebo-AMG 334) is greater than or equal to 75% then randomization will be stopped and it will be concluded that AMG 334 is effective in blocking PACAP-38 induced MLA.
- 4. If none of the first 3 decision rules apply at the interim analysis, an additional 20 subjects will be randomized in the trial. At the end of trial, if the p-value from the one-sided Fisher's Exact test is less than 0.1, it will be concluded that AMG 334 is effective in blocking MLA (TRIAL SUCCESS –LATE), or if the p-value from the one-sided Fishers Exact test is greater than or equal to 0.1, it will be concluded that AMG 334 is ineffective at blocking MLA.

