10.1 General Principles

Unless otherwise stated, data from PACAP-38 responders who go on to be randomized and receive IP will be summarized. Data from PACAP-38 non-responders, and data from

Statistical Analysis Plan: 20140207

Date: 17 May 2017 Page 22

PACAP-38 responders that do not receive IP, will not be included in the summaries, but will be reviewed.

Unless otherwise specified, data will be summarized using the safety analysis set, by actual treatment group (AMG 334 or Placebo).

Descriptive statistics will be provided for selected demographics, safety and PK data. Descriptive statistics on continuous measurements will include means, medians, standard deviations (and standard errors for post-baseline data), quartiles, and ranges, while categorical data will be summarized using frequency counts and percentages. Where statistical models are applied to the data, estimates of the differences/ratios, confidence intervals and corresponding p-values will be presented, as applicable. However, these are for descriptive and illustrative purposes only and to aid interpretation of the data; no formal statistical hypothesis testing will be performed.

When data are summarized by time, the values recorded against the scheduled time points, including any time windows specified in the protocol will be used.

When assessing minimum/maximum increases or decreases over the study, all assessments, including unscheduled assessments will be used.

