10.7 Exploratory Endpoint(s)

10.7.1 Migraine-like Attacks (MLA) and Headaches

The reduction in severity of MLA and headaches by AMG 334 within 24 hours after infusion of PACAP-38 on day 8 will be assessed and summarised based on a severity score (0-10; 0=pain free; 10=extreme pain). Severity of MLA and headaches will be analysed separately using a repeated measure analysis of variance model. Independent variables will be treatment, hour, and treatment by hour interaction. Subject will serve as a random effect. For each treatment by hour combination, least square means, ratio to placebo, 95% confidence intervals and corresponding nominal p-values for the null hypothesis of no difference from placebo will be presented. Graphical summaries of severity scores will also be provided. For SAS code, see Appendix A1.

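### The primary endpoint has no planned risk difference or confidence interval, yet a one-sided Fisher p of 0.1 or more is read as AMG 334 being ineffective; for moderate effects that negative is often unsupported.

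*SAP*

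**What the plan says.** SAP 10.5 defines the whole primary analysis in two sentences: "The number and percent of subjects experiencing a MLA within 24 hours after PACAP-38 infusion will be summarized for each treatment group", and "Comparison of PACAP-38 ability to produce MLA between AMG 334 and placebo will be done using the Fisher's Exact test". Protocol 10.5.2 (in the version dated 01 September 2016) has the same content. Neither names a risk difference, an odds ratio or an interval.

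SAP 10.1 has a general clause on estimation: "Where statistical models are applied to the data, estimates of the differences/ratios, confidence intervals and corresponding p-values will be presented, as applicable". It is tied to models and qualified, so it does not clearly reach a Fisher test on a two-by-two table. By contrast, SAP 10.7.1 asks explicitly for "least square means, ratio to placebo, 95% confidence intervals and corresponding nominal p-values" for the exploratory severity scores.

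The decision rules are in SAP 8.2 and Protocol 10.4.1. Under rule 4 the trial succeeds "if the p-value from the one-sided Fisher's Exact test is less than 0.1". Otherwise, if the "one-sided Fishers Exact test is greater than or equal to 0.1, it will be concluded that AMG 334 is ineffective at blocking MLA". Rule 2 also concludes that the drug is ineffective, at the interim, when at least 4 of 8 placebo subjects have an attack and the AMG 334 count is higher. It uses no p-value. Rule 1 stops for too few placebo attacks, and its conclusion concerns PACAP-38, not AMG 334.

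**The concern.** A non-significant Fisher test at 18 per arm can mean that the drug does nothing, or that the trial could not tell. Rule 4 has no outcome for the second case, and the planned primary output contains no interval that would separate the two.

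Protocol 2.5 gives the main objective as finding out whether the PACAP-38 and CGRP pathways are independent or whether CGRP lies downstream. An ineffective verdict would naturally be read as evidence for independence. Partial blockade is where the two readings diverge most, and the plan tabulates partial-blockade scenarios itself.

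**Working it through.** **Inputs** (SAP 3.2 and 8.2)
- Interim at 8 per arm; 10 more per arm if the trial continues, so 18 per arm at the end.
- Rule 1: stop if placebo attacks are 3 or fewer of 8.
- Rule 2: stop if placebo attacks are 4 or more and the AMG 334 count is higher.
- Rule 3: stop for success if the difference is at least 75%, that is 0.75 × 8 = 6 subjects.
- Rule 4: final success if one-sided Fisher p < 0.1.
- Scenarios: placebo 70%; AMG 334 20%, 35%, 50% or 70%.

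**Method.** Exact enumeration. Interim counts are independent Binomial(8, rate). Paths that continue add independent Binomial(10, rate) counts. With x placebo and y AMG 334 attacks at the end, p = P(H ≥ x), where H is hypergeometric: 18 draws from 36 subjects containing x + y attacks.

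**Step 1: reproduce the plan's table, then split the failures (placebo 70%).**

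| AMG 334 rate | Success, plan | Success, exact (early + late) | Rule 1 stop | Rule 2 stop | Rule 4 ineffective | Rules 2 + 4 |
|---|---|---|---|---|---|---|
| 20% | 91% | 19.5 + 71.4 = 91.0%* | 5.8% | 0.2% | 3.1% | 3.3% |
| 35% | 72% | 6.8 + 65.3 = 72.0%* | 5.8% | 2.2% | 20.0% | 22.2% |
| 50% | 38% | 1.6 + 35.8 = 37.4% | 5.8% | 9.7% | 47.0% | 56.8%* |
| 70% | 5% | 0.1 + 5.1 = 5.2% | 5.8% | 33.7% | 55.3% | 89.0% |

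*Summed before rounding.

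The plan's success figures are reproduced. For 38% v 37.4%, the simulation standard error with 10,000 trials is √(0.38 × 0.62 / 10,000) = 0.5 points. In the last row the drug has no effect, so a negative conclusion there is correct.

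**Step 2: what such a negative looks like.** Take 12/18 on placebo and 8/18 on AMG 334.
- Fisher one-sided p = 0.157, so rule 4 says ineffective.
- Difference: 0.667 − 0.444 = 0.222.
- Wilson 95% limits: placebo 0.437 to 0.837; AMG 334 0.246 to 0.663.
- Newcombe lower limit: 0.222 − √[(0.667 − 0.437)² + (0.663 − 0.444)²] = −0.094.
- Newcombe upper limit: 0.222 + √[(0.837 − 0.667)² + (0.444 − 0.246)²] = 0.484.

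The interval runs from −9 to 48 points, almost reaching the design effect of 70 − 20 = 50 points. With one fewer AMG 334 attack (12/18 v 7/18) p = 0.091, the difference is 28 points with a 95% interval of −4 to 53, and the verdict becomes effective.

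**Step 3: which interval to report.** An 80% interval might seem the natural partner of a one-sided 0.1 test. For 12/18 v 8/18 the Newcombe 80% interval is 1 to 41 points. It excludes zero while p = 0.157, so it would contradict the prespecified test.

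**The case against.** **The trial is built for a large effect.** It is. At 70% v 20% a false ineffective conclusion has about a 3% chance. A reader might infer that any working drug would often be declared ineffective; the documents do not support that. The risk becomes substantial only for effects smaller than the design effect.

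**The failure rates are not all rule 4.** Correct. Treating everything short of success as a verdict of ineffective would wrongly count rule 1 stops, which conclude something about PACAP-38. The 22% and 57% also include rule 2; rule 4 alone gives 20% and 47%.

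**The risk is already disclosed.** The success tables show 72% and 38%, and SAP 3.2 says that the sample size does not come from a power calculation. This stands as a defence of the design. It does not defend wording that turns a known chance of missing an effect into a conclusion of no effect.

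**The counts are reported, so anyone can compute an interval.** True, and the decision rules do not need one. But the plan neither commits to an interval nor fixes a method, and Step 3 shows that the method matters.

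**Rule 4 does not claim proof.** A reader might infer that it does. The text says only that "it will be concluded that AMG 334 is ineffective at blocking MLA", and SAP 10.1 adds that "no formal statistical hypothesis testing will be performed". That sentence weakens a reading as proof, but it sits awkwardly beside a rule that draws a conclusion from a p-value.

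**The example is chosen.** With 12/18 on placebo, 8/18 is the non-significant result closest to the threshold. It shows what rule 4 permits, not a typical negative.

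**Conclusion.** The point holds in a limited form. No effect estimate or interval is specified for the primary endpoint, and rule 4 states a negative conclusion that a p-value of 0.1 or more cannot carry by itself. A false ineffective conclusion under rule 4 has about a 3% chance at 70% v 20%, 20% at 70% v 35%, and 47% at 70% v 50%. With rule 2 the last two become 22% and 57%.

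The design, the sample size, the 0.1 threshold and the stated 91% are not in question. This is a fault in reporting and in the wording of a conclusion, but it bears directly on the pathway question that the trial exists to answer.

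Assumptions: a true placebo rate of 70%; no dropout, as none is given; ties at the interim continue, as rule 2 is worded; and Newcombe intervals, which are this review's choice and take no account of the interim stopping rules.

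**What to change.** 1. In SAP 10.5, add the risk difference (placebo minus AMG 334) with a 95% confidence interval by one prespecified method, either Newcombe or exact unconditional. State that the interval is descriptive, is not adjusted for the interim stopping rules, and does not override the Fisher decision.
2. Do not add an 80% Newcombe interval as the counterpart of the one-sided 0.1 test, because it can contradict that test.
3. In rule 4 (SAP 8.2 and Protocol 10.4.1), replace the conclusion of ineffective with efficacy not demonstrated, to be read with the interval. Make the same change in rule 2; changing rule 4 alone would leave 9.7 of the 56.8 points at 70% v 50% untouched.

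The cost is one line of output and a wording change in two rules. Thresholds, sample size and success probabilities stay as they are. The downside is a less clear-cut negative conclusion.

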10.6 Secondary Endpoint(s)

10.6.1 Number of Headaches

The number and percent of subjects experiencing a headache within 24 hours after PACAP-38 infusion will be summarized for each treatment group. Comparison of PACAP-38 ability to produce headaches between AMG 334 and placebo will be done using the Fisher's Exact test.

10.6.2 Safety Endpoints

10.6.2.1 Adverse Events (AEs)

The Medical Dictionary for Regulatory Activities (MedDRA) version 19.1 or later will be used to code all AE to a system organ class and a preferred term. The subject incidence of AEs will be summarized for all treatment-emergent, serious treatment-emergent, those leading to withdrawal of IP, fatal, and events of interest (EOI), where treatment refers to IP. The identification of EOI is a continuous process. Events may be identified and documented as the safety profile of the drug is characterized. The severity of each AE will be graded using common terminology for AE (CTCAE) version 4.0 criteria.

Statistical Analysis Plan: 20140207

Date: 17 May 2017 Page 24

Subject incidence of all treatment-emergent, serious treatment-emergent, those leading to withdrawal of IP, and fatal AE will be tabulated by system organ class and preferred term, where treatment refers to IP. Where appropriate, the tables will also be presented by worst grade. The above AE tables will not be created if two or fewer subjects experience the AE. The above AE tables will be summarized separately for events occurring between Day 1 and Day 7 following administration of IP and events occurring from Day 8 onwards following administration of IP and the second dose of PACAP-38.

For PACAP-38 related treatment-emergent AEs, all treatment-emergent AEs where the question "Is there a reasonable possibility that the event may have been caused by PACAP-38?" is ticked "yes" will be summarized by treatment group.

Details of each AE will be listed.

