9.2.2 Adverse Events

9.2.2.1 Reporting Procedures for Adverse Events That do not Meet Serious Criteria

The investigator is responsible for ensuring that all adverse events observed by the investigator or reported by the subject that occur after first dose of investigational product through the EOS are reported using the Adverse Event CRF.

The investigator must assign the following adverse event attributes:

- Adverse event diagnosis or syndrome(s), if known (if not known, signs or symptoms)
- Dates of onset and resolution (if resolved)
- Severity
- Assessment of relatedness to investigational product
- Action taken

The adverse event grading scale used will be the Common Terminology Criteria for Adverse Events (CTCAE). The grading scale used in this study is described in Appendix A. The investigator must assess whether the adverse event is possibly related to the investigational product, and/or other protocol-required therapies. This relationship is indicated by a "yes" or "no" response to the question: Is there a reasonable possibility that the event may have been caused by the investigational product, and/or other protocol-required therapies?

The investigator must assess whether the adverse event is possibly related to any study mandated activity (eg, administration of investigational product, protocol-required therapies, device(s) and/or procedure (including any screening procedure(s)). This relationship is indicated by a "yes" or "no" response to the question: "Is there a reasonable possibility that the event may have been caused by a study activity (eg, administration of investigational product, protocol-required therapies, device(s)), and/or procedure"?

The investigator is responsible for reviewing laboratory test results and determining whether an abnormal value in an individual study subject represents a clinically significant change from the subject's baseline values. In general, abnormal laboratory findings without clinical significance (based on the Investigator's judgment) are not to be recorded as adverse events. However, laboratory value changes that require treatment or adjustment in current therapy are considered adverse events. Where applicable,

clinical sequelae (not the laboratory abnormality) are to be recorded as the adverse event.

The investigator is expected to follow reported adverse events until stabilization or reversibility.

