10.5.3.2 Safety Endpoints

Subject incidence of adverse events will be summarized by system organ class and preferred term for all treatment-emergent, serious treatment emergent, IP related, those leading to withdrawal of investigational product, fatal, and of special interest (if applicable). The identification of adverse events of special interest is a continuous process. Events may be identified and documented as the safety profile of the drug is characterized.

Vital signs will be listed and reviewed for each subject. Depending on the size and scope of change in vital signs, summaries may be provided.

For ECGs measurements following PACAP-38, summaries over time and/or changes from baseline over time will be provided for all ECG parameters. Baseline will be defined measurements taken on Day 8 Pre-Dose. A subject's maximum change from baseline in QTcF and QTcB will be categorized and the number and percentage of subjects in each treatment group will be summarized. A subject's maximum post baseline values will also be categorized and the number and percentage of subjects in each treatment group will be summarized.

Hematology, biochemistry, and urinalysis data will be listed and reviewed for each subject. Values outside the normal laboratory reference range will be flagged as high or low on the listings. Depending on the size and scope of changes in laboratory data, summaries of laboratory data over time and/or changes from baseline over time may be provided.

Subject incidence of treatment-emergent suicidal ideation and behaviour as assessed by C-SSRS will be listed.

Binding antibody and neutralizing antibody formation will be assessed at predose and at various time points throughout the study including EOS. Antibody data will be listed for each subject. The incidence and percentage of subjects who develop anti-AMG 334 antibodies (binding and if positive, neutralizing) at any time may be tabulated.

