10.11 Exposure to Concomitant Medication

All medication will be coded using the World Health Organization Drug (WHO DRUG) dictionary. All prior and concomitant medications will be reviewed.

11. Changes From Protocol-specified Analyses

Minor changes to the protocol-specified analyses have been made and clarified in this SAP.

The safety analysis set has been modified slightly to include all subjects who receive IP (AMG 334 or placebo), but excludes any reference to whether the subject receives PACAP-38 or not. This is to take into account any subjects that receive IP, but do not receive PACAP-38 (eg, subject withdrew from the study before PACAP-38 could be administered). In these cases, the subject's data will be reviewed, but will not be included in any data summaries.

ECG data will not be summarized as specified in the protocol, as the data was collected as part of the standard of care and not in a thorough manner.

12. Literature Citations / References

Headache Classification Subcommittee of the International Headache Society. The international classification of headache disorders, 2nd edition. *Cephalalgia*. 2004; 24(Suppl. 1):8-160.

13. Data Not Covered by This Plan

The following analyses will be analyzed outside of this SAP:

- The changes in plasma PACAP-38 and CGRP concentrations pre- and post-dosing with AMG 334
- Blood samples collected for biomarker development

Statistical Analysis Plan: 20140207 Date: 17 May 2017 Page 27

14. **Appendices**

Statistical Analysis Plan: 20140207

Date: 17 May 2017 Page 28

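### SAP 10.6.2.1 omits the IP-related AE summary set out in the supplied protocol and adds a two-or-fewer rule that would usually remove the separate serious, withdrawal and fatal AE tables; SAP Section 11 declares neither change.

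*SAP*

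**What the plan says.** Protocol 10.5.3.2 plans subject incidence broken down by system organ class (SOC) and preferred term. It gives the categories as "for all treatment-emergent, serious treatment emergent, IP related, those leading to withdrawal of investigational product, fatal", with a further category for events of special interest. It sets no minimum number of affected subjects.

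SAP 10.6.2.1 lists its AE categories twice. The opening summary sentence reads "The subject incidence of AEs will be summarized for all treatment-emergent, serious treatment-emergent" and goes on to withdrawal of IP, fatal events and events of interest. The table sentence reads "Subject incidence of all treatment-emergent, serious treatment-emergent, those leading to withdrawal of IP, and fatal AE will be tabulated by system organ class", with preferred terms shown within each class. IP-related events are in neither list. Soon after the table sentence comes the threshold: "The above AE tables will not be created if two or fewer subjects experience the AE". These tables are also to be produced separately for Days 1 to 7 and for Day 8 onward.

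A summary by treatment group is then specified for PACAP-38-related events, selected by the question "Is there a reasonable possibility that the event may have been caused by PACAP-38". It comes after the threshold sentence and carries no threshold of its own. The section ends by providing a listing of every AE.

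SAP Section 11 states "Minor changes to the protocol-specified analyses have been made and clarified in this SAP". The changes it describes concern the safety analysis set and the ECG summaries.

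**The concern.** The safety and tolerability of AMG 334 is a secondary objective, and treatment-emergent AEs are a secondary endpoint. As written, the SAP summarizes events attributed to the challenge agent but not events attributed to the study drug. The data for the missing summary should exist, because Protocol 9.2.2.1 makes relatedness to IP one of the attributes the investigator must assign to each AE.

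The threshold is a second and independent matter. In a randomized part of 16 to 36 subjects, two affected subjects can be a sizeable share of one arm. Serious, withdrawal and fatal events are the categories most likely to have counts of one or two, so they are the ones the rule removes. A listing keeps the events but does not give the incidence by arm that the protocol describes.

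**Working it through.** **Side-by-side check of categories**

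| Category | Protocol 10.5.3.2 | SAP 10.6.2.1 |
|---|---|---|
| All treatment-emergent | yes | yes, threshold applies |
| Serious | yes | yes, threshold applies |
| IP related | yes | absent from both lists |
| Leading to withdrawal of IP | yes | yes, threshold applies |
| Fatal | yes | yes, threshold applies |
| PACAP-38 related | yes (10.5.4.2) | yes, no threshold |

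The missing IP-related row does not depend on any count: no such table is planned at all.

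**How often the threshold would act**

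The documents give no figure for this, so there is nothing to reproduce. Inputs:
- Randomized N is 16 or 36, allocated 1:1, giving 8 or 18 per arm (SAP 3.1, 3.2 and 8.2).
- A table is dropped at two or fewer affected subjects (SAP 10.6.2.1).
- The event rate r is an assumption. For orientation, the three Phase 1 studies in Protocol 2.2.2.1 to 2.2.2.3 report serious AEs in 0 of 60, 2 of 48 and 0 of 32 subjects. That is 2/48 = 4.2% in the one study with any, and 2/140 = 1.4% pooled.

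Let X be the number of affected subjects in both arms together, X ~ Bin(N, r), with independent subjects, the same rate in both arms and no split by period. The case that matters is a table dropped although something happened:

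P(dropped | at least one event) = [P(X=1) + P(X=2)] / [1 − P(X=0)]

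At r = 5%:
- N = 16: P(0) = 0.95^16 = 0.440; P(1) = 16 × 0.05 × 0.95^15 = 0.371; P(2) = 120 × 0.05² × 0.95^14 = 0.146. Result: (0.371 + 0.146) / (1 − 0.440) = 0.92.
- N = 36: P(0) = 0.95^36 = 0.158; P(1) = 36 × 0.05 × 0.95^35 = 0.299; P(2) = 630 × 0.05² × 0.95^34 = 0.275. Result: (0.299 + 0.275) / (1 − 0.158) = 0.68.

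Range over r:

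| r | N = 16 | N = 36 |
|---|---|---|
| 1.4% (2/140) | 0.993 | 0.964 |
| 2% | 0.987 | 0.932 |
| 4.2% (2/48) | 0.945 | 0.760 |
| 5% | 0.923 | 0.682 |
| 10% | 0.741 | 0.271 |

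Setting the formula equal to 0.5 gives r of about 15.6% at N = 16 and 7.0% at N = 36. Below those rates, a table with at least one event is more likely than not to be dropped.

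**What one dropped table can hide**

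A 2 versus 0 split is 2/8 = 25% versus 0%, or 2/18 = 11% versus 0%. Both fall under the threshold.

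**The case against.** There is a fair case that little is lost, and several stronger readings do not survive it.

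- **That every AE table is suppressed.** The PACAP-38-related summary lies outside the rule. All 7 of the early Part A subjects described in Protocol 2.4 had a treatment-emergent AE, so the all-TEAE table from Day 8 onward will rarely fall to two subjects.
- **That serious events would have no incidence by arm.** This depends on wording the SAP leaves open. If the threshold covers only the SOC and preferred-term tables, the opening summary sentence still yields an overall count of serious, withdrawal and fatal events. If it removes whole tables, a serious event still appears by preferred term in the all-TEAE table, and the listing identifies it as serious. If it works term by term, a term affecting two subjects could drop out there too, leaving only the listing. It is also unclear whether the count is taken per period, which would drop more.
- **That small counts are why AMG 334-related events go uncounted.** They are not; the table is simply not planned.
- **That AMG 334 effects cannot be separated from challenge effects.** Both arms receive PACAP-38, so the randomized comparison of all TEAEs isolates AMG 334 without any causality judgment. The Day 1 to 7 tables also precede the post-treatment challenge.
- **That attribution fails at collection.** A reader might infer this from the Protocol 9.2.2.1 question about an event "caused by the investigational product, and/or other protocol-required therapies", and expect nearly every answer to be yes. But the same section lists relatedness to IP as its own attribute, and the SAP uses a PACAP-38-only question. The documents do not support asking for the question to be split.
- **That an undeclared departure from the governing protocol is proven.** The SAP implements Amendment 4 (21 October 2016), while the supplied protocol is Amendment 3 (1 September 2016). The mismatch is shown only against the latter.

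These arguments narrow the point. They do not supply the IP-related summary, settle what the threshold covers, or explain its absence from Section 11.

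**Conclusion.** The point holds in limited form. Against Amendment 3, the SAP drops the IP-related incidence summary and adds a threshold the protocol does not contain, and Section 11 mentions neither. No AMG 334-related count by arm is planned, whatever the frequency.

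Separately, the threshold would usually remove the stand-alone serious, withdrawal and fatal tables. Given at least one event at an assumed 5% rate, it does so in 92% of trials at N = 16 and 68% at N = 36. At 10% and N = 36 the figure is 27%, so usually does not hold there. The figures pool both arms, assume independent subjects with a common rate, apply the rule to whole tables and ignore the split by period.

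The events themselves are not lost, since every AE is listed. What is lost is a routine statement of n/N by arm for the categories that matter most to a safety reader.

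**What to change.** In SAP 10.6.2.1:

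1. Add a summary of IP-related treatment-emergent AEs by arm, by SOC and preferred term as in Protocol 10.5.3.2, using the relatedness-to-IP attribute already collected.
2. Exempt serious, withdrawal-of-IP, fatal and IP-related AEs from the two-or-fewer rule, or limit the rule to their SOC and preferred-term breakdown, so that n/N (%) by arm is always reported.
3. If the rule is kept elsewhere, say whether it removes a table or a term, and whether the count is per period.

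Check Amendment 4 for its list of AE categories, and record any remaining departure in SAP Section 11.

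The cost is SAP wording and a few short tables, some of them nearly empty. This write-up asks for no change to data collection.
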